6.2 Healthy Skin Grafts

We will identify optimal harvesting sites on the body of recipient. Although the epidermal collection is essentially painless (donor will feel warmth and mild pressure at the site) and leaves infrequent, mild scarring and/or hypopigmentation we will not choose intensely exposed locations, such as head, neck, palms and soles. The primary collection site is often the thigh, but as skin is developmentally, structurally and functionally different at different parts of the body we will attempt collection of epidermis from a general area on the recipient's body that corresponds to the site of the wound being treated. Of course, we are prepared to adapt to physical specifics and psychological choices of the recipient. For Arm B enrollees, grafts will be taken from sites without history of blistering.

6.3 Epidermal Transfer

The grafting will be done in real time. This FDA approved (Regulation number 878.4820) operating procedure will be followed in all details to collect the donor epidermis from a maximum of 3 sites at one sitting and to transfer it to up to 3 regions in the recipient location. Grafts will be secured with bandages and protected for at least 2 weeks, and preferably up to 3-4 weeks if possible. Patients are educated on how to re-apply grafts that have fallen off (i.e. cleanse with saline and re-apply if < 2 weeks and no obvious contaminate of the graft),, although it is not presumed to be detrimental if these grafts are not in place the full 2-4 weeks. Wounds will be observed for any signs of infection, photographed weekly (along with the respective "control" wounds) as able.

6.4 Subsequent Wound Treatment

It is recognized that most participants will have additional wounds (including the control lesions from the initial treatment event) which could benefit from healthy tissue grafting. Patients will be offered treatment of up to 3 additional regions if at least 12 weeks has passed since the last treatment, if there were no unacceptable outcomes from previous graft procedures and if the original donor is available. Subsequent treatments would not contribute to the primary and secondary study endpoints, but data will be collected in a similar fashion including weekly photographs (as able) for clinical care and follow-up of wound BSA with wound BSA analyzed ideally at 6 and 12 weeks (as well as additional follow-up timepoints for other treatment sessions/clinical care) for publication.

Patients who have additional wounds that could benefit from CelluTome after one year of treatment with no significant adverse events attributable to the CelluTome procedure will be offered to extend treatment and re-enroll for an additional year. Re-consent would then occur with each annual follow-up if the patient wishes to extend treatment with the intent of collecting data for publication; otherwise subsequent sessions could be completed off-protocol as compassionate care without data collection for publication. If additional wounds are treated the original schedule (i.e. 1 year follow-up) will be adhered to as the 1st set of treated/control wounds are for the study endpoints. Subsequent wound treatment will be treated as an independent event (i.e. start as a new day 0) and the schedule in section 8 will serve as a guideline, therefore deviations from this schedule for subsequent treatment sessions will not be considered protocol deviations. Because subsequent treatments will not contribute to the study endpoints, follow-ups (weeks 6 and 12, at 1 year), may be performed remotely or at a medical facility closer to home with the results sent to our institution. Although it is recommended the patient return for follow-up assessment at approximately 12 weeks and 1 year post initial grafting session, remote or local follow-up will be allowed.

7 Expected Risks

7.1 Donor

We do not expect any significant side-effects as this procedure has been accepted as safe in the field and used for treatment of number of skin conditions, such as vitiligo and diabetic leg ulcers, with an excellent safety profile.¹⁶⁻¹⁹ Of note, though the harvested tissue (epidermis) does not cross the basement membrane, the procedure is essentially painless (donor will feel warmth and mild pressure at the site) and there is infrequent, mild scarring and/or hypopigmentation, we will still examine the sites of epidermal harvest via weekly photographs until healed (as able) and at 12 weeks as able for any abnormalities detectable by physical examination.

7.2 Recipient

Even though the graft and recipient are uniquely and fully HLA matched, there can be local (and much less likely systemic) effects of grafting. Most prominent among these is non-engraftment (sloughing off the graft) because of subclinical infection, ongoing fibrosis and—related to that—inadequate vascular supply at the recipient site. This can be accompanied by local inflammation with systemic febrile reaction, though none would be expected to be serious adverse events.

8 Schedule of Events

8.1 Patient (Recipient – Arm A/re-enrollments Arm C)

	Prior to CelluTome Treatment	Day Of Harvest (Day 0)	Weekly Until 12 Week Visit ³	6 Weeks (+/- 1 Week) ⁵	12 Weeks (+/- 1 Week) ⁶	1 Year (+/- 3 Months) ⁶
Written consent	X					
Physical exam		X		X	X	X
Identification by physical exam and documentation of EB wounds ¹		X				
Donor chimerism	X ⁷					
Photographs of the targeted lesions (and “control” lesions as able)		X anytime between baseline and harvest	X by parent or caretaker via iphone or similar device	X	X	X
Transfer of the epidermal micrografts from donor to the recipient sites		X				
Assessment of adverse events		X		X	X	X
Quality of life - itch and pain scales, (iscorEB) ²		X		X	X	X
Research skin biopsies ⁸				X		

1 – a maximum of 3 EB regions will be identified for treatment with additional wounds considered controls (as able). If there are no significant side effects, control wounds and/or other wounds may be treated after a minimum of 12 weeks of observation after the initial grafting per section 6.4.

2 –testing/procedures may be waived, if performed recently as part of follow-up on an EB treatment protocol (i.e. MT2009-09 or MT2015-20) or as standard of care, if the results are available for this study. Will attempt collection of full iscorEB at annual visits in accordance with standard of care, but at minimum, patient portion is requested for analysis of pain and itch.

3 – If possible

4 – footnote deleted

5 -May be conducted remotely through UMN provider or the patient's home/local provider if physical assessment indicated and the patient is unable to return to UMN

6- Ideally at UMN site unless patient is absolutely unable to return, in which case local or remote assessment should be completed with results sent to the PI and study staff

7- Peripheral blood donor chimerism should be measured within 21 days of grafting and be $\geq 5\%$ and stable.

Stability of chimerism will be determined by the protocol team and based on 3 peripheral blood chimerism values at least 1 month apart

8 – Three 4mm punch biopsies (optional) at a grafted site to examine immunofluorescence, electron microscopy, and donor engraftment taken at time of routine sedated procedure during the 1-year follow-up time period.

8.2 Donor (Arm A)

	Prior To CelluTome Treatment	Day Of Harvest (Day 0)	Weekly Until The Week 12 Visit ¹	6 Weeks And 12 Weeks (+/- 1 Week) ²	1 Year (+/- 3 Months) ²
Written consent	X				
Brief assessment	X			X	X
Donor infectious disease panel	X ³				
Identification and documentation of harvesting sites (maximum of 3 sites)		X			
Epidermal harvesting		X			
Photographs of harvest sites		X (pre)	X by parent or caretaker via iphone or similar device	X	
Assessment of adverse events		X		X	X

1 – if possible; not needed once harvest site is healed per PI.

2 - Donors may be assessed remotely if unable to return to primary site

3 - Within 30 days of harvest

8.3 Patient (Self Donor – Arm B/re-enrollments Arm D)

	Prior To CelluTome Treatment	Day Of Harvest (Day 0)	Weekly Until The Week 12 Visit ³	6 Weeks And (+/- 1 Week) ⁵	12 Weeks (+/- 1 Week) ⁶	1 Year (+/- 3 Months) ⁶
Written consent	X					
Physical exam				X	X	X
Identification by physical exam and documentation of EB wounds ¹		X				
Baseline skin biopsy of unaffected (possibly revertent or mosaic) site and affected site to confirm somatic reversion ²	X					
Identification and documentation of harvesting sites	X					
Photographs of the targeted lesions, ("control" lesions, and harvest sites as able)	X anytime between baseline and harvest		X by parent or caretaker via iphone or similar device	X	X	X

	Prior To CelluTome Treatment	Day Of Harvest (Day 0)	Weekly Until The Week 12 Visit ³	6 Weeks And (+/- 1 Week) ⁵	12 Weeks (+/- 1 Week) ⁶	1 Year (+/- 3 Months) ⁶
Epidermal harvest and transfer of the epidermal micrografts to the targeted lesions		X				
Assessment of adverse events		X		X	X	X
Quality of life , itch and pain scales (iscorEB) ²	X anytime between baseline and harvest			X	X	X
Research skin biopsies ⁷			X			

1 – a maximum of 3 EB regions will be identified for treatment with additional wounds considered controls (as able). If there are no significant side effects, control wounds and/or other wounds may be treated after a minimum of 12 weeks of observation after the initial grafting per section 6.4.

2 –testing/procedures may be waived, if performed recently as part of follow-up on an EB treatment protocol (i.e. MT2009-09 or MT2015-20) or as standard of care, if the results are available for this study. Will attempt collection of full iscorEB at annual visits in accordance with standard of care, but at minimum, patient portion is requested for analysis of pain and itch.

3– If possible

4 – footnote deleted

5 - May be conducted remotely through UMN provider or the patient's home/local provider if physical assessment indicated and the patient is unable to return to UMN

6- Ideally at UMN site unless patient is absolutely unable to return, in which case local assessment should be completed with results sent to the PI and study staff

7 – Two 4mm punch biopsies (optional) at a grafted site to examine immunofluorescence, electron microscopy, at time of routine sedated procedure during the 1-year follow-up time period.

9 Adverse Event Monitoring, Recording and Reporting

Toxicity and adverse events will be classified according to NCI's Common Terminology Criteria for Adverse Events V 4.0 (CTCAE) and reported on the schedule below. A copy of the CTCAE events can be downloaded from http://ctep.cancer.gov/protocolDevelopment/electronic_applications/ctc.htm#ctc_40

9.1 Event Monitoring/Documentation of Donor Sites and Recipient Sites

Event monitoring will focus on: 1) the areas from which the skin cells are harvested and 2) the sites to which the skin cells are applied for signs of poor healing (inflammation, sloughing of skin) with or without systemic fever.

Any adverse event, CTCAE v 4 \geq grade 3 and felt to be at least possibly related to the epidermal grafting procedure will be documented in OnCore. The trial will halt enrollment and be re-evaluated if a grade 4 (CTCAE v4) skin related event occurs in any one of the treated lesions per section 12.4 and is at least possibly related to the epidermal grafting procedure.

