1.5 Interim Results as of September 2018

Interval assessment completed in September of 2018 included 9 DEB subjects enrolled on Arm A. No subjects have been treated on Arm B. Assessment of the initial round of CelluTome grafting for the first 9 subjects on Arm A included a total of 18 grafted wounds. The mean decrease in wound surface area at 12 weeks post-grafting was 85.6% (range 24.4-100%). Eight wounds assessed at 1 year post-grafting showed a mean decrease in wound surface area of 85.6% (range 44-100%). Donors universally had no scarring. Given these remarkable responses, we amended the protocol to allow for re-consenting and data collection on additional rounds of grafting for enrolled subjects lacking adverse events after 1 year on study.

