1.7 Study Objectives

The **primary** study objective is to achieve > 50% wound closure as measured on a per wound basis within 12 weeks of skin grafting.

Secondary objectives are to:

1. assess safety, longevity and functionality of grafted skin in the recipient at 1 year
2. measure changes in quality of life (QOL) through pain, itching and general QOL questionnaire via iscorEB assessment score
3. safety and seamless, scar-free healing of the body sites of the donor from which epidermis has been harvested over the period of 1 year

2 CelluTome® Epidermal Harvesting System

The CelluTome® is a vacuum device that is applied to an area of skin and left on for approximately 30 minutes. Via gentle negative pressure, it slowly raises a series of small (millimeters in diameter), thin epidermal skin grafts that are then sheared off via a disposable blade within the apparatus. The grafts then adhere to a square of non-adhering silicone mesh dressing and are ready for grafting to another site. A similar piece of silicone mesh is then applied to the area of harvested skin as a wound dressing. Refer to appendix III for an overview of the process.

While similar devices have existed for years, the Cellutome has several novel transformative properties.¹⁶⁻¹⁹ Harvesting causes only possible mild discomfort (warmth and pressure), infrequent, mild scarring and/or hypopigmentation , and results in minimal

(if any) bleeding for the donor. Further, the device is significantly more automated and yields much more standardized grafts than prior iterations of this device. The potential for operator error or suboptimal specimens during blister grafting has been significantly diminished.

3 Study Overview

This is a single-institution pilot study to determine the capacity of immune-syntonic epidermal grafting to achieve > 50% wound closure as measured on a per wound basis within 12 weeks of skin grafting in individuals with the generalized severe forms of epidermolysis bullosa, DEB and JEB. Up to 3 uninfected regions (or infected regions if previously treated prior to grafting) will be identified for treatment with similar size wounds identified as controls if possible (no treatment).

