10.1 Data Management

This study will report clinical data using The Online Enterprise Research Management Environment (OnCore™), a web based Oracle® database utilizing study specific electronic case report forms. Key study personnel will be trained on the use of OnCore and will comply with protocol specific instructions embedded within the OnCore forms. Patient demographics, patient specific study treatment calendars, adverse events, reporting of deaths, and other information will be placed in OnCore. The iScorEB results will be recorded in the BMT database. All biopsy results and photographs will be maintained and stored under the supervision of the PI.

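### Section 9.1 watches for sloughing, inflammation and fever at any grade, but the only events it requires to be documented are related ones of grade 3 or higher, so milder reactions need not enter the safety data

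*Combined protocol and SAP*

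**What the plan says.** - **What is watched (section 9.1).** Harvest sites and grafted sites are monitored "for signs of poor healing (inflammation, sloughing of skin) with or without systemic fever". No grade is attached.
- **What must be documented (section 9.1, next paragraph).** The rule applies to an adverse event of CTCAE version 4 grade at or above "grade 3 and felt to be at least possibly related to the epidermal grafting procedure will be documented in OnCore". Severity and attribution must both be met.
- **What is expected (section 7.2).** Non-engraftment, meaning that the graft sloughs off, is named as the most prominent recipient effect. The section adds: "This can be accompanied by local inflammation with systemic febrile reaction, though none would be expected to be serious adverse events". For donors, sections 6.2 and 7.1 name mild scarring or hypopigmentation as an infrequent effect.
- **What the study sets out to learn (section 1.7).** The recipient objective is to "assess safety, longevity and functionality of grafted skin in the recipient at 1 year". The donor objective is "safety and seamless, scar-free healing of the body sites of the donor from which epidermis has been harvested", followed for a year. Section 12 makes early information on safety part of the study's purpose.
- **What goes into the database (section 10.1).** "adverse events, reporting of deaths, and other information will be placed in OnCore", with no grade or relatedness condition.
- **What is analysed (section 12.3).** Only the iscorEB. No safety summary is described.

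**The concern.** The reactions that the plan names and watches for are of a kind that can easily stay below grade 3, and the one rule on documentation starts at grade 3. It also requires a judgement of relatedness. A reaction at an untreated control wound can hardly be attributed to the grafting, so treated and control wounds cannot be compared on local reactions from the documented events.

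What is at stake is the meaning of the safety result. If the database holds few or no events at the end, a reader will want to know whether mild sloughing, inflammation and fever were rare or were not entered. Under the current text that question may have no answer. The donor side has the same gap: the objective is scar-free healing, yet a mild scar does not meet the threshold.

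**Working it through.** The plan states no figure on this point, so there is nothing to reproduce. The check is a reading of every section that deals with adverse events, followed by an illustration under stated assumptions.

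**Step 1. The named findings against the rule in section 9.1.**

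| Finding | Must be documented under 9.1? | Where else it may show |
|---|---|---|
| Related local reaction or fever, grade 3 or higher | Yes | – |
| Local inflammation, grade 1–2 | No | Examinations; weekly photographs where obtained |
| Graft sloughing, grade 1–2 | No | Photographs; 12-week wound area if closure suffers |
| Fever, grade 1–2 | No | Visit assessment; a photograph cannot show it |
| Any grade, judged unrelated | No | As above |
| Mild scar or hypopigmentation at a harvest site | No | Photographs and examination; the Arm A donor schedule (8.2) marks no photograph at 1 year, only a brief assessment and an adverse event assessment |

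**Step 2. Does another section close the gap?**

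- Section 9, opening: events are classified by CTCAE. It does not say that every grade is entered.
- Section 8: adverse events are assessed on Day 0, at 6 and 12 weeks and at 1 year. It does not say what is recorded from the assessment.
- Section 9.2: prompt reporting to the IRB is aimed at matters such as unanticipated effects, new risks or events that force a protocol change. The reactions in section 7.2 are anticipated.
- Section 10.1: adverse events are listed among the database contents. This neither repeats nor lifts the threshold.
- Sections 10.1 and 11: photographs are reviewed for adverse events and stored under the investigator's supervision. They are not described as coded safety data.
- Section 12.3: no safety table. Section 12.4: acts only on grade 4 or higher.

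No section expressly requires a grade 1–2 or unattributed reaction to become safety data.

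**Step 3. Illustration.** The patient numbers, n = 25 in Arm A and n = 10 in Arm B, come from section 12.1. The documents give neither r, the share of patients with a related local reaction, nor g, the share of those reactions that reach grade 3. I assume r from 10% to 40% and g from 0% to 20%, independent patients, one reaction counted per affected patient, and the strict reading in which lower grades are not entered.

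- Affected = n·r; documented = n·r·g; undocumented = n·r·(1 − g); chance of an empty record = (1 − r·g)^n.
- Arm A, r = 20%, g = 10%: affected 25 × 0.20 = 5; documented 5 × 0.10 = 0.5; undocumented 4.5; chance of an empty record 0.98^25 = 0.60.
- Arm A, fewest undocumented (r = 10%, g = 20%): 25 × 0.10 × 0.80 = 2. Most (r = 40%, g = 0%): 25 × 0.40 = 10.
- Chance of an empty record, Arm A: from 0.92^25 = 0.12 (r = 40%, g = 20%) to 1.00 (g = 0%). Arm B: from 0.92^10 = 0.43 to 1.00.
- If 0 of 25 patients in Arm A had a documented event, the exact two-sided 95% upper limit would be 1 − 0.025^(1/25) = 13.7%. It would bound related events of grade 3 or higher and nothing milder.

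The width of these ranges shows that the size of the loss rests on the assumptions and not on the documents.

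**The case against.** The strongest reply is that section 9.1 never says that nothing else is documented. Section 10.1 is unqualified, and the instructions embedded in the electronic forms are not available to the reader. This stands in part: exclusivity is an inference. But a specific threshold beside a general list leaves the site free to enter or omit mild events, and uneven entry is no better for a safety table.

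Four stronger readings are tempting, and the documents do not support them.

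- A reader might infer that the plan cannot capture these reactions at all, or that the safety result is near zero by construction. Related reactions of grade 3 or higher are documented. Examinations and photographs show some of the rest. Non-engraftment that matters for closure would show in the 12-week wound area, which is judged by a blinded reviewer with no grade or attribution filter. The wound area is still not a record of sloughing, since section 6.3 does not regard early loss of the graft as necessarily harmful.
- A reader might infer from section 7.2 that all the expected reactions lie below grade 3. Seriousness and CTCAE grade are different scales, so the sentence makes this plausible and does not prove it.
- A reader might infer that further grafting and re-enrolment are decided on a truncated database. Section 1.5 describes the amendment as allowing "data collection on additional rounds of grafting for enrolled subjects lacking adverse events after 1 year on study", and section 6.4 sets the operative conditions. Neither says that the decision is taken from OnCore, and patients are examined at scheduled visits.
- A reader might take the unblinded judgement of relatedness as a serious bias. Possible relatedness is a low bar, and grafting can hardly be concealed from the patient or the treating team. What remains is that the filter leaves unattributed events out of the required record.

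It is also fair to say that limited adverse event capture can be a reasonable choice in a pilot of an approved device. That supports keeping the threshold for other events. It does not support applying it to the very reactions that section 9.1 singles out.

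**Conclusion.** The point holds as a gap between what is monitored and what must be documented, together with an unreconciled difference between sections 9.1 and 10.1. Followed as written, the recipient and donor safety objectives would rest mainly on related events of grade 3 or higher. Milder or unattributed sloughing, inflammation and fever, and mild donor-site scarring or hypopigmentation, need not enter the safety data. Section 12.3 defines no safety table in which they could appear.

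The number of reactions missed cannot be derived from the documents. The 2 to 10 patients in Arm A shown above follow from assumed rates and the strict reading of section 9.1. If the site in fact enters every grade, the loss is smaller and the remedy is clarification. The change is worth making because it is cheap and lets the study answer its own safety objectives. Neither the primary endpoint nor its analysis is affected.

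**What to change.** In section 9.1, and in matching words in section 10.1, state that:

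- at the existing 6-week, 12-week and 1-year visits, any graft sloughing or non-engraftment, local inflammation or local infection since the previous visit is recorded in OnCore for each treated wound, and for each control wound where applicable;
- at the same visits, any poor healing, scarring or hypopigmentation is recorded for each harvest site, and fever is recorded for each patient or donor;
- these entries are made at every CTCAE grade, with attribution as a separate field and not as a condition for entry;
- events on the day of the procedure are recorded on Day 0;
- all other events keep the current threshold.

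Asking about the interval since the previous visit matters because a brief reaction may have resolved by week 6. Weekly photographs, where available, can support the answer.

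In section 12.3, add a descriptive table of these events by arm, per wound and per patient, with a separate part for donors.

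The cost is a few sentences in sections 9.1, 10.1 and 12.3, a short checklist on the existing visit forms, slightly more data entry and one more table. No visit or procedure is added. The safety profile will look less clean, which is the price of its being informative.
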